6. METHODS AND ASSESSMENTS

6.1. Randomisation and Blinding

The study will be open-label since our primary endpoint is an objective pharmacokinetic parameter.

Treatment allocation between the Atorvastatin + Omeprazole and Atorvastatin only arms will be generated by a random allocation sequence using real-time web-based randomization system (IVRS) in a 1:1 ratio. Our desired allocation ratio (1:1) can be achieved using permuted block randomization. Block randomization ensures balance between the 2 groups, in which the order of allocation is chosen at random at the beginning of the block. Block size will be determined by the study team member.

Intervention group 1: Atorvastatin 40mg/day + Omeprazole 20mg/day

Control group: Atorvastatin 40mg/day

We target to recruit 78 patients, of whom 39 patients will be assigned to each of the 2 treatment arms. The pharmacist will dispense the IP to the study participants. Each participant will be supplied 30 tablets of Atorvastatin and those in the intervention arm will receive an additional 30 capsules of Omeprazole during the trial. A total of 60 tablets / capsules will be dispensed to each participant in the intervention arm and 30 tablets to each participant in the control arm. An additional 5 surplus tablets / capsules of each drug will also be supplied to replace any damaged or missing tablets / capsules. Atorvastatin and Omeprazole will all be packaged and coded by the manufacturer. The pharmacist will be provided with the code list and will dispense the IP to each participant based on the unique subject ID for that participant. A CRC will provide a prescription on the day of the study visit and ensure that it is kept at the appropriate storage condition prior to administration.

6.2. Study Visits and Procedures

The total study duration is 31 days and consists of 2 study visits (Fig. 1). Blood samples will be collected at each timepoint (T1 and T2) for metabolic panel and biomarker measurements. All blood sampling (B) are study activities and not routine medical care.

Study Visit T1 (Day 0)

This will be the screening and enrolment visit. Estimated duration is 90 mins. The following procedures will be performed during this visit:

[figure not shown]
- i) Confirming eligibility and Informed consent taking (30 minutes)
- ii) Completion of demographic + medical + medication history survey (10 minutes)
- iii) Blood sample collection (10 minutes)
- iv) Post-collection health monitoring (20 minutes)
- v) Randomization, distribution of drugs and explain how to take the assigned medications (20 minutes)

Study Visit T2 (Day 30)

T2 will be follow-up visit 30 days after intervention. Estimated duration is 60 mins. The following procedures will be performed during this visit:

- i) Self-reported compliance questionnaire and return of unused drugs if any (20 minutes)
- ii) Blood sample collection (10 minutes)
- iii) Post-collection health monitoring (20 minutes)
- iv) Reimbursement (10 minutes)

Figure 1 SEACOL Study protocol

a. Post Study Follow up and Procedures

There will not be post study follow-up or procedures.

b. Discontinuation Visit and Procedures

The last study visit (T2) should be done if withdrawal occurs. Participants may withdraw voluntarily from the study at any time and for any reason without penalty. This will not affect their routine medical care. If voluntary withdrawal occurs, the participant should be asked to continue scheduled evaluations, complete an end of study evaluation and be given appropriate care under medical supervision until the symptoms of any adverse event resolve or until the participant's condition stabilizes. The PI may also withdraw the patient's participation in the study at any time if they decide that it is in the patient's best interests or if they have other medical problems.

The reasons for withdrawal or discontinuation will be documented in the participant's Case Report Form. In the case of any premature withdrawal from the study, blood samples and study data that have been collected up to the time of withdrawal or discontinuation will be kept and analysed as intention-to-treat analysis.

c. Measurements

- 1) Demographic + medical + medication history survey on the first visit. Information to be collected include: age, gender, race, history of liver or kidney disease, whether a statin or proton pump inhibitor has been taken in the past 30 days, any diagnosed medical condition and regular medications, as well as whether the participant is taking any supplements, traditional or herbal products.
- 2) Blood sample collection (18mL each time x 2 times, on enrolment and after 30 days of intervention).
- 3) Consumption of investigational drugs (Atorvastatin or Atorvastatin + Omeprazole)
- 4) Self-reported compliance questionnaire at the second visit timepoint. Questions include: (i) Have you missed taking the medications on any day(s) during the 30 days study period? (Yes / No. If yes, please state how many days: ___); (ii) How many tablets / capsules have you been taking each day? (___)
- 5) LC-MS measurement: Blood samples will be processed to extract plasma. Plasma samples, calibrators and quality control samples will be transferred into a deep well 96-well plate and standard curve will be used for quantification of Atorvastatin lactone levels in the plasma samples.
- 6) hs-CRP and lipid panel assays on participant's plasma samples using cobas c-111 machine

7. TRIAL MATERIALS

7.1. Trial Product (s)

Both drugs are US FDA and Singapore HSA approved drugs.

(i) Atorvastatin is a synthetic lipid-lowering agent, which is an inhibitor of HMG-CoA reductase. This enzyme catalyzes the conversion of HMG-CoA to mevalonate, an early and rate-limiting step in cholesterol biosynthesis. Atorvastatin is indicated as an adjunct to diet for reduction of elevated total-cholesterol (total-C), low density lipoprotein cholesterol (LDL-C), apolipoprotein B (apo B) and triglycerides (TG) in adults, adolescents and children aged 10 years or older with primary hypercholesterolemia, heterozygous familial hypercholesterolemia or

combined (mixed) hyperlipidaemia (Fredrickson Types IIa and IIb), elevated serum triglyceride (TG) levels (Fredrickson Type IV), and for patients with dysbetalipoproteinemia (Fredrickson Type III) when response to diet and other non-pharmacological measures is inadequate. Atorvastatin is also indicated to reduce total-C and LDL-C in adults with homozygous familial hypercholesterolemia as an adjunct to other lipid-lowering treatments (e.g. LDL apheresis) or if such treatments are unavailable. Atorvastatin is also indicated to reduce the risk of myocardial infarction (MI) in adult hypertensive patients without clinically evident coronary heart disease (CHD), but with at least three additional risk factors for CHD such as age \geq 55 years, male sex, smoking, left ventricular hypertrophy, other specified abnormalities on electrocardiogram (ECG), microalbuminuria or proteinuria, ratio of plasma total cholesterol (total-C) to HDL-cholesterol \geq 6, or premature family history of CHD. Atorvastatin is indicated in adults with type 2 diabetes and without clinically evident CHD, but with multiple risk factors for CHD such as retinopathy, albuminuria, smoking or hypertension, as well as in adults with clinically evident CHD.

(ii) Omeprazole is a proton pump inhibitor which suppresses gastric basal and stimulated acid secretion by inhibiting the parietal cell H⁺/K⁺ ATP pump. Omeprazole is indicated for the treatment of gastroesophageal reflux disease (acute, healing or symptomatic), heartburn, helicobacter pylori eradication, peptic ulcer disease, duodenal or gastric ulcers and Zollinger-Ellison syndrome.

There is a possibility that subjects may suffer from an allergic reaction to Atorvastatin and / or Omeprazole or even suffer from adverse effects to Atorvastatin. The risk of elevated serum transaminases with Atorvastatin 40mg is 0.6%. The risk of rhabdomyolysis, a severe form of muscle injury, resulting from Atorvastatin therapy is about 0.5 – 1.0% over 5 years.

7.2. Storage and Drug Accountability

Both drugs have similar storage requirements, with reference to their individual product information leaflet. The drugs need to be stored in a cool and dry place, away from direct sunlight, at or below 30°C. Specifically for Atorvastatin, it should also be stored in its original aluminium blister to protect from moisture. Hence, if we are packaging Atorvastatin tablets in bottles for the subjects, a moisture absorber should be included in the bottle, such as a packet of silica gel, and subjects should be reminded not to remove that moisture absorber as well as to minimize exposure of the medication to moisture.

8. TREATMENT

8.1. Rationale for Selection of Dose

The proposed dosing used is 40mg/day for Atorvastatin and 20mg/day for Omeprazole, which are within approved therapeutic ranges (Atorvastatin 10 - 80mg, Omeprazole 20 - 360mg). The chosen doses are also the commonly prescribed doses for each drug based on clinical experience, with well-documented safety and efficacy profile.

8.2. Study Drug Formulations

Atorvastatin is formulated as oral tablets while Omeprazole is formulated as oral capsules.

8.3. Study Drug Administration

Since Atorvastatin is dosed once daily while Omeprazole can be dosed once or twice a day, for convenience and to improve compliance, we decided to schedule both drugs for once a day administration. Omeprazole should preferably be taken on an empty stomach, such as 30 - 60 mins before breakfast, while Atorvastatin can be administered without regard to food, hence, to standardize administration across all treatment arms, we will advise patients to take their assigned drugs 30 mins before breakfast.

8.4. Specific Restrictions / Requirements

The risk of myopathy during treatment with Atorvastatin (HMG-CoA reductase inhibitor) is increased with concurrent administration of cyclosporine, fibric acid derivatives, lipid-modifying doses of niacin or CYP 3A4/transporter inhibitors (e.g., erythromycin and azole antifungals). These medications should be avoided during the study period or spaced at least 2 – 4 hours apart from Atorvastatin if not possible to omit.

The Omeprazole and Clopidogrel combination is a well-known drug interaction whereby Omeprazole may diminish the antiplatelet effects of Clopidogrel due to Omeprazole-mediated inhibition of CYP2C19, an enzyme responsible for clopidogrel metabolism to its active metabolite. Nonetheless, clinical evidence has suggested limited impact on clinical efficacy for using this drug combination and it is still a popularly prescribed pair of drugs, but for the purpose of this study, we will advise against initiating Clopidogrel during the study period.

8.5. Blinding

The study will be open-label.

8.6. Concomitant therapy

All medications (prescription and over the counter), vitamin and mineral supplements, and / or traditional or herbal products taken by the participant should be documented.

9. SAFETY MEASUREMENTS

9.1 Collecting, Recording and Reporting of “Unanticipated Problems Involving Risk to Subjects or Others” – UPIRTSO events to the NHG Domain Specific Review Boards (DSRB)

UPIRTSO events refers to problems, in general, to include any incident, experience, or outcome (including adverse events) that meets ALL of the following criteria:

1. Unexpected

In terms of nature, severity or frequency of the problem as described in the study documentation (eg: Protocol, Consent documents etc).

2. Related or possibly related to participation in the research

Possibly related means there is a reasonable possibility that the problem may have been

caused by the procedures involved in the research; and

3. Risk of harm

Suggests that the research places participants or others at a greater risk of harm (including physical, psychological, economic, or social harm) than was previously known or recognized.

Reporting Timeline for UPIRTSO Events to the NHG DSRB.

1. Urgent Reporting: All problems involving local deaths, whether related or not, should be reported immediately – within 24 hours after first knowledge by the NHG investigator.
2. Expedited Reporting: All other problems must be reported as soon as possible but not later than 7 calendar days after first knowledge by the NHG investigator.

9.2 Collecting, Recording and Reporting of Serious Adverse Events (SAEs) to the Health Science Authority (HSA)

1. For Principal Investigator initiated Trials

All SAEs that are unexpected and related to the study drug must be reported to HSA.

“A serious adverse event or serious adverse drug reaction is any untoward medical occurrence at any dose that:

- Results in death.
- Is life-threatening (immediate risk of death).
- Requires inpatient hospitalization or prolongation of existing hospitalization.
- Results in persistent or significant disability/incapacity.
- Results in congenital anomaly/birth defect.
- Is a Medically important event.

Medical and scientific judgment should be exercised in determining whether an event is an important medical event. An important medical event may not be immediately life threatening and/or result in death or hospitalization. However, if it is determined that the event may jeopardize the subject and/or may require intervention to prevent one of the other adverse event outcomes, the important medical event should be reported as serious.”

All SAEs that are unexpected and related to the study drug will be reported. The investigator is responsible for informing HSA no later than 15 calendar days after first knowledge that the case qualifies for expedited reporting. Follow-information will be actively sought and submitted as it becomes available. For fatal or life-threatening cases, HSA will be notified as soon as possible but no later than 7 calendar days after first knowledge that a case qualifies, followed by a complete report within 8 additional calendar days.

9.3 Safety Monitoring Plan

Safety assessments during the study include monitoring the wellbeing of each study participant regarding any adverse events he/she may experience. All study participants receiving treatment will be attended by the site PI if any medical issues arise.

Regular reports on conduct and progress of the project will be provided by the study team to the Domain Specific Review Board (DSRB) ethics committees and to the team of investigators. The team of investigators will conduct random inspections of the research procedures, data and consent documentation, which includes the checking of the completeness of the Investigator File and verifying data collection forms. In addition, the Investigators will ensure the integrity of the data through the following strategies:

- Regular project meetings (monthly) with project progress (written and verbal) and dedicated time for discussion and intellectual exchange (monthly)
- Rotation of meetings among different sites to enable easy attendance
- Use of secured shared IT procedures to allow investigators and collaborators from the different organizations and sites to access shared databases.

9.4 Complaint Handling –

All complains or feedback about this research study will either be dealt with by the Principal Investigator and/or the NHG Domain Specific Review Board Secretariat. Participants will be notified in the patient information consent form to contact the PI if they have any questions, complaints or concerns. In addition, they can also contact the NHG Domain Specific Review Board Secretariat at [name] if they want an independent opinion to discuss problems and questions, obtain information and offer inputs on their rights as a research subject.

10 DATA ANALYSIS

10.1 Data Quality Assurance

LC-MS metabolite quantification as well as hs-CRP and lipid panel assays will be done in duplicates or triplicates to ensure accurate and reproducible results.

10.2 Data Entry and Storage

Data collected and entered in the Case Report Forms (CRF) and questionnaires will be stored in a secure location at the main study site (NUS CVRI). A patient coded electronic database containing data extracted from the Case Report Forms will also be securely stored. Only the research team will have access to the Case Report CRF or any medical data. In the event of any publication regarding this study, the data will be de-identified so that the identity of the patient remains confidential.

11 SAMPLE SIZE AND STATISTICAL METHODS

11.1 Determination of Sample Size

We aim to assess the effect size of a minimum clinically significant difference in Atorvastatin lactone concentration of 1.68µg/L for the Atorvastatin + Omeprazole group compared to the Atorvastatin monotherapy group. Goh et al. 2023 reported a 1.4 times higher ATVlac in patients who were on ATV + OMP and literature on the pharmacokinetics of ATV reported the C_{max} of ATVlac to be 4.2 ± 2.4 µg/L following oral administration of ATV 40mg. By inference, we expect a ATVlac concentration of $4.2 \times 1.4 = 5.88$ µg/L in the ATV + OMP arm

and this equates to a difference of 1.68µg/L in ATVlac concentration compared to the ATV monotherapy arm. Using a 2-sample t-test at a power (1-beta) of 85% and one-sided significance level (α) of 95%, we will need 30 subjects per treatment arm. To account for 30% drop-out after randomization, we will need to recruit at least 39 subjects per treatment arm and a total of 78 subjects for the study.

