2.2. Primary Objectives

To investigate the effect of co-administration of Omeprazole with Atorvastatin versus Atorvastatin monotherapy on atorvastatin lactone level.

Primary endpoint: Higher statin lactone level in intervention arm (Atorvastatin + Omeprazole) after 30 days

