3. STUDY POPULATION

3.1. List the number of subjects to be enrolled.

We aim to assess the effect size of a minimum clinically significant difference in Atorvastatin lactone concentration of 1.68µg/L for the Atorvastatin + Omeprazole group compared to the Atorvastatin monotherapy group. Goh et al. 2023 reported a 1.4 times higher ATVlac in patients who were on ATV + OMP and literature on the pharmacokinetics of ATV reported the C_{max} of ATVlac to be 4.2 ± 2.4 µg/L following oral administration of ATV 40mg. By inference, we expect a ATVlac concentration of $4.2 \times 1.4 = 5.88$ µg/L in the ATV + OMP arm and this equates to a difference of 1.68µg/L in ATVlac concentration compared to the ATV monotherapy arm. Using a 2-sample t-test at a power (1-beta) of 85% and one-sided significance level (α) of 95%, we will need 30 subjects per treatment arm. To account for 30% drop-out after randomization, we will need to recruit at least 39 subjects per treatment arm and a total of 78 subjects for the study.

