5. STUDY DESIGN

5.1. Summary of Study Design

This is a 2-arm, prospective, randomized, parallel-group, open-label, longitudinal study that lasts 30 days for each study participant. Assessment of primary and secondary outcomes have been planned in an exploratory setting.

Fig. 1 shows the study protocol.

Table 1 shows trial plan and procedure to be conducted on each study visit.

2. Description of study visits:

a) Pre-screening, consenting process, and screening procedures

Potential subjects will be identified through (i) direct advertisement such as posters to be put up around NUS / NUH, (ii) indirect – through word or mouth or snowballing. Participants who are interested will be interviewed over the phone by the study's Clinical Research Coordinator (CRC). During the telephone interview, participants will be given a brief description of the study design and procedures to be followed. If the participant is eligible, with their verbal agreement, arrangement will be made for them to visit NUHS IMU (located in NUS MD6, level 7) for a screening and enrolment visit.

b) Informed consent

Informed consent will be taken by the PI. The study will be explained to the participant in detail. This will be performed in the privacy of a closed-door room. During the consenting process, the study will first be explained to the participants and ample time will be provided for patients to read through the informed consent form. They will also be (i) given opportunity to clarify any doubts before acknowledging the consent form; (ii) allowed to return home to discuss their participation with their family prior to consenting. Non-English speakers will have the English informed consent form with a short consent form in their language, so that they can understand the purpose of this study and what is required of them. If the participant agrees to participate, the informed consent form will be signed by

the PI and the participant, in the presence of a prescribed witness. In the event that the participant is illiterate, or a short consent form will be used, an impartial witness will be present instead. A copy of the informed consent will be kept by both the PI and the participant. Enrolled subjects will be updated in the Screening and Enrolment Log. Unselected subjects will be documented in the Pre-screening Log.

(c) Screening and baseline data collection

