Participants who have signed the informed consent form will be assessed for eligibility to participate, based on the following assessments: (i) Demographic data; (ii) Medical and medication history; (iii) history of adverse drug reactions (if any). Patients will be interviewed directly to provide the above health information; medical records will not be assessed. Based on the collected data, approval for participation will be finalised by either the PI or Co-PI. Participants who are eligible for the study will be informed by the CRC and enrolled as a subject for the study.

(d) Blood draw

Post-fasting (8 hours) whole blood will be drawn twice. 18mL will be collected by ventipuncture each time, once at the time of recruitment (before intervention) and a second time on the second visit (T2) 30 days after the start of the intervention period. This amounts to a total of 36mL of blood collected throughout the study period. Blood will be drawn into EDTA vacutainers. All samples will be transferred from NUHS IMU to the PI's research laboratory (located in [name] lab, NUS MD6, level 8). All the blood will be spun down to plasma. With an estimated plasma extraction efficiency of 45% via centrifugation, we expect to obtain about 8.1mL of plasma from 18mL of blood. The plasma will be aliquoted and stored in a -80 degrees Celsius freezer until analysis. For atorvastatin lactone metabolite profiling, a 1mL aliquot will be subjected to protein precipitation and used for analysis. Another 1mL aliquot will be used for high sensitivity c-reactive protein (hs-CRP) assays using the cobas c-111 machine. Another 3mL of plasma will be used for lipid panel profiling using cobas c-111 machine. The remaining plasma samples will be stored at -80 degrees Celsius for repeated analysis, if necessary.

3. Randomization and treatment allocation

The study will be open-label since our primary endpoint is an objective pharmacokinetic parameter.

Treatment allocation between the Atorvastatin + Omeprazole and Atorvastatin only arms will be generated by a random allocation sequence using real-time web-based randomization system (IVRS) in a 1:1 ratio. Our desired allocation ratio (1:1) can be achieved using permuted block randomization. Block randomization ensures balance between the 2 groups, in which the order of allocation is chosen at random at the beginning of the block. Block size will be determined by the study team member.

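### The sample size rests on a literature peak level, but the primary endpoint is one fasting day-30 level whose time from the last dose is neither fixed nor recorded in the visible text

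*Protocol*

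**What the plan says.** **Planning basis.** Protocol section 11.1, repeated in section 3.1, starts from a published peak: "literature on the pharmacokinetics of ATV reported the C_{max} of ATVlac to be 4.2", with SD 2.4 µg/L. It multiplies the mean by a ratio of 1.4 from an earlier study, introducing the result with "By inference, we expect a ATVlac concentration of", and reaches 5.88 µg/L and a difference of 1.68 µg/L. With a one-sided two-sample t-test and 85% power it asks for 30 per arm.

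**Endpoint.** Section 2.2 defines the primary endpoint as "Higher statin lactone level in intervention arm (Atorvastatin + Omeprazole) after 30 days". Section 11.2 compares the arms at the second visit with a one-sided t-test.

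**Sampling.** Section 5.1, under the blood draw, says "Post-fasting (8 hours) whole blood will be drawn twice": once before treatment and once at T2. There is therefore one on-treatment sample per participant. Section 6.2 places it by day only: "T2 will be follow-up visit 30 days after intervention".

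**Dosing.** Section 8.3 ties the dose to a meal: "we will advise patients to take their assigned drugs 30 mins before breakfast".

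**Records of dosing.** Section 6.2 lists a "Self-reported compliance questionnaire at the second visit timepoint". That questionnaire (Appendix 4) asks about missed days and the number of units taken per day. It carries a date and time field for the form itself. The T2 procedures, the list of measurements and the schedule in Appendix 1 have no entry for the clock time of the last dose.

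**The concern.** A peak is the highest point of a concentration profile. One sample cannot identify it, and the T2 sample is not timed to approach it. A participant who doses on the morning of the visit and then gives blood before eating has kept the fast and followed the dosing advice. So has one who gives blood first and doses afterwards. The first sample is taken soon after a dose and the second about a day after one, and the two would be analysed together as the same quantity.

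Two things are at stake:

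- **Precision.** Mixing samples from different times after dosing adds spread to the only on-treatment measurement. If the hour of the last dose is not written down, no later analysis can adjust for it.
- **Meaning of the power statement.** The mean and SD behind the stated 85% belong to a peak. Nothing in the protocol shows that the same relative spread, or the same ratio of 1.4, holds at the T2 draw.

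**Working it through.** **Inputs from section 11.1.** Control mean 4.2, SD 2.4, ratio 1.4, one-sided test, power 85%, 30 per arm. The significance level is printed as 95% and is read here as 5%. All power figures use the exact noncentral t distribution for a pooled two-sample t-test with a common SD in both arms.

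**Step 1: reproduce the plan.**
- Difference = 4.2 × 1.4 − 4.2 = 5.88 − 4.2 = 1.68 µg/L.
- Standardised difference = 1.68 / 2.4 = 0.70.
- Required n = 30.04 per arm; power at 30 per arm = 84.95%.

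The stated 30 per arm is reproduced.

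**Step 2: express the plan without units.** The difference is 0.4 of the control mean, and the control CV is 2.4 / 4.2 = 0.571. The standardised difference is therefore 0.4 / CV. If mean and SD at the T2 draw are both lower than at the peak by the same factor, the CV is unchanged and power stays at 85%. So a lower level alone does not matter; the CV and the ratio at the draw do.

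**Step 3: vary the CV.** The documents give no CV for a T2 sample, so the values above 0.571 are assumptions. The ratio is held at 1.4 and n at 30 per arm.

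| Control CV at the draw | 0.4 / CV | Power |
|---|---|---|
| 0.571 (peak, from the plan) | 0.700 | 85% |
| 0.70 (assumed) | 0.571 | 71% |
| 0.80 (assumed) | 0.500 | 61% |
| 1.00 (assumed) | 0.400 | 45% |

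**Step 4: what mixed timing could do.** Suppose a share p of draws is pre-dose, at a fraction r of the post-dose level, with CV 0.571 within each kind of draw and the ratio of 1.4 holding for both. In units of the post-dose control mean:

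- mean m = p·r + (1 − p)
- CV = √[(p·r² + 1 − p)(1 + 0.571²) − m²] / m

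Worked case, p = 0.5 and r = 0.5: m = 0.75; p·r² + 1 − p = 0.625; CV = √(0.625 × 1.3265 − 0.5625) / 0.75 = 0.688; 0.4 / 0.688 = 0.581; power 72%.

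Both p and r are assumed. With p = 0.5:

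| r | Mixture CV | Power at 30 per arm |
|---|---|---|
| 0.8 | 0.586 | 83% |
| 0.7 | 0.607 | 81% |
| 0.5 | 0.688 | 72% |
| 0.25 | 0.897 | 53% |

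The loss runs from about 2 points to over 30, depending on an r that the documents do not give.

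**The case against.** **Nothing in the documents conflicts.** A reader might infer that the fasting draw and the dosing instruction contradict each other. They do not: dosing before breakfast fits an 8-hour fast whether the draw comes before or after the dose. The text is silent on the order. That stands, and the point is an open choice, not a contradiction.

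**Part of the evidence is not shown.** Figures 1 and 2 and the case report form are missing from the copy reviewed and could set a window or hold a dose time. This also stands. Confidence is high on the peak-based planning, which is printed text, and medium on the absence of a window.

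**Draw time may already be captured.** The Appendix 4 form has a date and time field, and section 6.2 lists the 20-minute questionnaire directly before the draw. If that order is kept, the field approximates the draw time. Only the time of the last dose has no visible place.

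**The trial may still have its power.** It may. Step 2 shows that 85% survives if the CV and the ratio carry over. One could obtain much lower figures by holding the SD at 2.4 while the mean falls to 75%, 50% or 25% of the peak, but that implies control CVs of 0.76, 1.14 and 2.29, and nothing in the documents suggests such spreads.

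**The harm is limited.** Section 5.1 says "Assessment of primary and secondary outcomes have been planned in an exploratory setting". Randomisation, with the same dosing advice in both arms, makes uncontrolled timing mainly a source of noise. This moderates the point but does not remove it: the protocol still states a power, and a dose time that was never recorded cannot be recovered.

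**Conclusion.** The concern holds in limited form. The planning figures describe a peak, the endpoint is one fasting T2 level, and the visible text neither fixes nor records how long after the last dose that level is taken. The stated 85% is not shown to apply to the endpoint. It does apply if the ratio of 1.4 and a CV of about 0.57 hold at the draw. Otherwise, with 30 per arm and a common SD, power is 71%, 61% or 45% at assumed CVs of 0.70, 0.80 or 1.00. With half the draws pre-dose, it runs from 83% to 53% as the assumed pre-dose level falls from 0.8 to 0.25 of the post-dose level.

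A reader might infer that 30 per arm is too few, or that the comparison is biased. The documents support neither: they give no mean, SD or CV for a T2 sample, and nothing in them points to different timing between arms. The supported conclusion is avoidable variance and a power statement not tied to what is measured. It should be fixed, but it does not invalidate the design.

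**What to change.** Before T2 visits begin:

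1. State one dose-to-draw window for T2, the same in both arms and consistent with the fasting text in section 5.1 and the dosing text in section 8.3. Which window to use is for the sponsor to decide.
2. Add the clock time of the last dose to the T2 form, and confirm that the draw time is recorded there.
3. In sections 3.1 and 11.1, say that the mean, SD and difference are based on a peak concentration, and give the power at 30 per arm over a stated range of CVs for the T2 sample.

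If the unseen figures or case report form already carry items 1 or 2, it is enough to repeat them in the text.

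**Cost.** One sentence on visit timing, one or two time fields and a revised sample-size paragraph. The downsides are a small scheduling burden and a stated power that may look less favourable. The change itself adds no participants.
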